Recent nonclinical in vitro and in vivo studies of the combination of M5717 and pyronaridine showed a positive interaction between the 2 drugs ([Rottmann 2020](#)). The chemopreventive activity of M5717 alone was assessed in a clinical, sequential, double-blind, randomized, placebo-controlled *P. falciparum* sporozoite challenge study (Study MS201618_0003). Single different doses of M5717 administered after direct venous inoculation of *P. falciparum* sporozoites to healthy adult malaria-naïve participants demonstrated a full protective effect at 100 mg and 200 mg, while at lower doses a delayed time to parasitemia was shown compared to placebo.

The efficacy, safety, and exposure of the combination of M5717 and pyronaridine in African adults and adolescent patients with acute uncomplicated malaria will be evaluated in a parallel Phase 2a study (Study MS201618_0033 [CAPTURE 1]).

[figure not shown]

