9.2 Sample Size Determination

Actively Enrolled Study Cohorts (Cohorts 1 to 4)

In total, 192 participants will be randomly assigned to study intervention with a ratio of 1:1:1:1 to Cohorts 1 to 4, such that approximately 180 evaluable participants are anticipated to be obtained assuming a drop-out rate < 10% as observed in other malaria studies. This will result in 45 participants per treatment cohort.

In order to investigate the time of protection of M5717 plus pyronaridine (see Section 2.1), it is important to show that with the highest dose of M5717 at least an effect comparable to Pyramax (pyronaridine+artesunate) over 63 days can be shown.

Within a clinical study by use of Pyramax for which results are reported in [Dabira 2022](#), 3 different dose regimens of Pyramax were compared with respect to number of patients with parasitemia over 63 days (1-, 2-, and 3-day regimen). For the 1 day regimen the same dose of pyronaridine as planned for this study was administered (540 mg/720 mg according to body weight) to asymptomatic individuals with *P. falciparum* infection. Out of 96 participants of the 1-day regimen arm 84.4% remained without parasitemia at Day 63. Since a slightly higher proportion of participants without parasitemia is expected for M5717 plus pyronaridine, a proportion of 87% will be assumed in the following.

In [Sukwa 1999](#) results of a randomized, double-blind, placebo-controlled field study to determine the efficacy of Malarone for prevention are reported. In this study, asymptomatic volunteers residing in a highly malarious area of Zambia were first treated with a 3 day treatment regimen of Malarone to clear all parasites (same approach as for Cohort 4 in this study). After liver and blood stage parasite cure, participants were randomized to receive daily treatment with either Malarone or Placebo over 70 days. In the Placebo group of 111 participants the proportion of participants without parasitemia at Day 70 was 63%.

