- **Death due to malaria or other reasons:** filter SAEs programmatically for fatal events with outcome "death" and by medical/safety review. Death cases for which the primary reason is ticked as "progressive disease and/or disease-related condition" qualify as death due to malaria. A composite variable strategy is applied if the death was due to malaria (i.e. a parasitemia event is considered at the time of death) and an on-treatment strategy is defined if death was due to other reasons (i.e. time to parasitemia is censored at the time of death)

The population-level summary is defined as the Hazard Ratios (HRs) for each dose of M5717 relative to the untreated participants in Cohort 4. HRs are estimated from a Cox Proportional Hazards Model with time to parasitemia included as the dependent variable and dose cohorts, site and sex included as independent factors, and baseline age, body weight and parasite density included as independent covariates. Participants will be censored in case of occurrence of an ICE as described above, at the last available visit in case of premature study discontinuation or at the end of study in case no parasitemia event was observed.

For the multivariable (primary) model, a table showing HRs together with 95% Wald CIs will be provided which will contain in addition estimates of coefficients, SEs and p-values (based on Likelihood Ratio Test) in order to assess whether the factors and covariates included into the model have a significant influence on the time to parasitemia. As additional information a table providing information on censoring frequency and occurrence of ICEs will be provided.

As part of descriptive analyses of the primary endpoint, which also covers the analysis of the second estimand (incidence of parasitemia), a table displaying number and percentages of

parasitemia events (estimated directly from the data) will be provided together with estimates of a Kaplan-Meier (KM) analysis. Median time of protection and 95% CI will be estimated using the KM method for each cohort. As a graphical illustration, a KM-figure will be provided showing time to parasitemia in days after parasite clearance.

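### The primary hazard ratios are to have Wald intervals, with no rule for a dose cohort that has no parasitemia events, where a Wald interval has no usable limits

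*SAP*

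**What the plan says.** The HR of each M5717 dose against Cohort 4 is the primary population-level summary (Protocol Sections 3 and 9.4.1.1; SAP Sections 5 and 14.1.1). SAP Section 14.1.1 estimates it from a Cox model with "dose cohorts, site and sex included as independent factors, and baseline age, body weight and parasite density included as independent covariates", and for that model "a table showing HRs together with 95% Wald CIs will be provided". The same table also carries likelihood-ratio p-values, whose stated purpose is "in order to assess whether the factors and covariates included into the model have a significant influence on the time to parasitemia".

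The model is used again in three places. SAP Section 14.1.3 adds age-group and country interactions and asks for 95% intervals without naming a type. Section 14.2.1 repeats all the primary analyses against the matched Pyramax cohort. Section 14.2.2 repeats them for the two PCR-adjusted endpoints.

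Neither document mentions a profile-likelihood, penalised or exact interval, or a rule for a cohort with no events. Section 14.1.1 does add event counts, percentages and Kaplan-Meier estimates by cohort.

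**The concern.** A Wald interval is the log HR plus or minus 1.96 standard errors. If a dose cohort has no events, the partial likelihood keeps rising as the HR falls to 0. There is then no finite log HR and no finite standard error, and what the software prints depends on where the iteration stops. The primary summary would have no usable interval for the dose with the best possible result. A substitute method would have to be chosen after the empty cohort had been seen, in an open-label trial.

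The other planned outputs do not fill the gap. The Kaplan-Meier median would not be reached, and a Greenwood-type interval has zero width when there are no events.

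**Working it through.** **Inputs.** Protocol Section 9.2 gives 1:1:1:1 allocation, and of the evaluable total it says "This will result in 45 participants per treatment cohort". It assumes 63% event-free in the control and 87% at the highest dose, an HR of 0.29, 21 events, and 80% power with 90 participants at α = 0.05.

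**The plan's own figure.** By Schoenfeld's formula with two-sided α, events = 4(1.96 + 0.842)² / (ln 0.29)² = 20.5, so 21. Power with 21 events is 81%. The stated figures are reproduced.

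**Planned events per cohort of 45.** Control: 45 × 0.37 = 16.65, taken as 17. Highest dose: 45 × 0.13 = 5.85, taken as 6.

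**Why the Wald interval fails with no events.** In a two-arm comparison, let r be the ratio of dose to control participants at risk at a control event. Up to a constant, the log partial likelihood is −Σ ln(1 + r·HR), which is largest at HR = 0. The information for the log HR is about HR × Σ r, which goes to 0.

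Take r ≈ 45/36.5 = 1.233, where 36.5 is midway between 45 and 45 − 17 = 28 controls at risk. If the iteration stops at log HR = −10, the information is about 17 × 1.233 × 0.0000454 = 0.00095, so the standard error is about 32.4. A full fit gave 32.7 and a Wald interval of about 7 × 10⁻³³ to 3 × 10²³. Stopping at −5 instead gives 0.00003 to 1.35. Neither interval describes the data.

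**What the profile interval gives.** The upper limit solves 2 Σ ln(1 + r·HR) = 3.84. With the same average r, ln(1 + 1.233·HR) = 1.92/17 = 0.113, so HR = 0.1196/1.233 = 0.097. The full fit gave 0.099.

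**Comparison by number of dose-arm events.** These are 45 per arm, 17 control events, weekly visits, full follow-up and no covariates, with one illustrative dataset per row:

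| Dose-arm events | HR | Wald 95% CI | Profile-likelihood 95% CI |
|---|---|---|---|
| 0 | 0 | no finite limits | 0 to 0.099 |
| 1 | 0.049 | 0.007 to 0.368 | 0.003 to 0.239 |
| 2 | 0.101 | 0.023 to 0.437 | 0.016 to 0.352 |
| 6 (about as planned) | 0.311 | 0.123 to 0.790 | 0.112 to 0.750 |

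**How likely an empty cohort is.** P(no events) = Sⁿ, where S is the true event-free proportion. Only 87% is a planning value; the other rows are assumptions. The 35 is the approximate minimum number of matches for the external comparison (Protocol Section 9.2; SAP Section 14.2.1).

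| S | n = 45 | n = 35 |
|---|---|---|
| 87% | 0.2% | 0.8% |
| 90% | 0.9% | 2.5% |
| 95% | 9.9% | 16.6% |
| 98% | 40.3% | 49.3% |

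If all three dose cohorts were at 87%, the chance that at least one is empty would be 1 − (1 − 0.0019)³ = 0.6%.

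**Subgroups.** Cell sizes are not given. At 87% event-free, an assumed dose cell of 6, 8, 12 or 15 participants is empty with probability 43%, 33%, 19% or 12%. The PCR-adjusted endpoints each count only part of the parasitemia events, so empty cohorts are likelier there too. The documents give no rates from which to put a number on that.

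**The case against.** Under the sponsor's own assumption the problem almost never arises: 0.87⁴⁵ is 0.2%. The study is exploratory and descriptive (Protocol Section 9.1), no decision rule depends on this interval, and 0 of 45 against about 17 of 45 would be plain from the event table. All of that stands, and it limits the weight of the point. It does not supply the missing interval for the primary summary.

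Four stronger readings are tempting, and the documents do not support them.

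- **An empty cohort is to be expected.** Protocol Section 2.2 says that single doses of M5717 alone "demonstrated a full protective effect at 100 mg and 200 mg". That was a sporozoite challenge in healthy, malaria-naïve adults. This trial follows infected residents of endemic areas through up to 63 days of natural exposure, and it counts recrudescence, rescue medication and malaria death as events. The challenge result is not a forecast for this setting.
- **The p-value will contradict the interval.** This assumes one likelihood-ratio test per coefficient. The stated purpose fits equally well with a joint 3-degree-of-freedom test of the four-level cohort factor, which need not agree with any single HR interval. Pairing Wald intervals with likelihood-ratio p-values is not an error in itself.
- **Simulated disagreement between test and interval is a further measure of the problem.** In two-arm simulations the likelihood-ratio test was significant without a Wald interval excluding 1 in about 11% of trials at 95% event-free. Without the empty arms this falls below 1%, so it is largely the same risk counted again. At 87% it is about 3%, nearly all of it borderline disagreement in arms that do have events.
- **Wald fails for any strongly protective dose.** With a single event the Wald interval is 0.007 to 0.368: wider than the profile interval, but usable.

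**Conclusion.** The point holds as a minor gap in pre-specification. If a dose cohort has no events, the stated interval for the primary HR has no usable limits, neither document has a fallback, and a standard alternative gives an informative upper limit (about 0.10 for 0 of 45 against 17 of 45). The divergence itself does not depend on the number of control events, the visit pattern or the covariates; the 0.10 does.

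The chance that it matters in the primary analysis is about 0.2% at the planned 87% and reaches about 10% only if true protection is near 95%. These probabilities treat the event-free proportion as binomial with complete follow-up. The reused analyses are more exposed, but how much depends on cell sizes and event splits that the documents do not give. Sample size, power and the planned comparisons are unaffected.

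**What to change.** In SAP Section 14.1.1, specify profile-likelihood instead of Wald intervals for the dose-cohort HRs. Suggested text: *Hazard ratios for the dose cohorts will be reported with 95% profile-likelihood confidence intervals. If a dose cohort has no parasitemia events, the hazard ratio will be reported as 0 with the profile-likelihood upper limit only (likelihood-ratio cut-off 3.84). The same rule applies to the subgroup, external-control and PCR-adjusted analyses in Sections 14.1.3, 14.2.1 and 14.2.2.* For subgroups, add that an HR is shown as not estimable if both cells are empty.

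Firth's penalised likelihood is optional. On the 0 of 45 example it gives an HR of 0.024 (0.0002 to 0.173), which helps if a non-zero point estimate is wanted, but the profile limit already works without it.

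The cost is a few sentences in the SAP before database lock and slightly more computation, with no new data. At about six dose-arm events the interval moves only from 0.123–0.790 to 0.112–0.750.

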14.1.2 Sensitivity Analyses of the Primary Estimand

As sensitivity analysis, an alternative strategy of handling the ICE “Experience of any event that affects absorption” is used. Instead of applying a treatment policy strategy, an on-treatment strategy is applied, i.e. the time to parasitemia is censored at the time the ICE occurred. If the ICE occurs prior to parasite clearance (the start time of survival analysis), the participants will be censored at the time of parasite clearance. All analyses as described within the previous section will be repeated unless the ICE did not occur. In case the sensitivity analyses will be conducted, the numbering of the outputs for the primary estimand will be split (i.e. 8.2.1.1 Analyses of Primary Estimand – Main Analysis; 8.2.1.2 Analyses of Primary Estimand – Sensitivity Analysis).

14.1.3 Subgroup Analyses of the Primary Estimand

In order to investigate treatment effects in predefined subgroups the Cox Proportional Hazards Model as described above is repeated by including age groups as defined in Section 8.2 and country as factors. Hazard Ratios and 95% confidence intervals for the subgroup levels will be obtained from the dose cohort and age group, and dose cohort and country main and interaction terms, respectively, which have to be included into the model. As a graphical presentation a forest plot of HRs by subgroups will be provided in addition.

14.2 Further Estimands

14.2.1 Parasitemia

To indirectly evaluate the additional time of protection of different doses of M5717 alone, the time to parasitemia as observed for Cohorts 1-3 will be compared to time to parasitemia from the Pyramax external control cohort. All analyses as described for the primary estimand will be repeated by comparing against the Pyramax external control cohort instead of the natural infection cohort. For this comparison only data of participants identified during the propensity score matching process (see Section 9.1) will be used.

If the number of identified matches is < 35, then the respective cohort will not be used for comparison to the synthetic control arm from the external study. If the number of matches is < 35 for all cohorts the use of the synthetic control arm will not be performed at all.

14.2.2 PCR-adjusted Parasitemia

For PCR-adjusted parasitemia (thick smear/microscopy, after adjustment for parasitemia due to new infections and due to recrudescence, respectively) the same analyses and outputs will be provided as for the primary estimand. For the derivation of the population-level summary the same ICEs and strategies are applied as for the primary estimand as described in Section 14.1.1.

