Visit Number	Prescreening	Scr + Visit 1 ^a	Visit 2 ^a	Visit 3	Visit 4	Visits 5 to 12	Visit 13	Unscheduled Visit	
^a Visit 1 and 2: Participants randomized to Cohorts 1 to 3 will remain in hospital or stay in the vicinity of the sites for 24 hours for PK sampling and assessment of parasitemia (see Table 2).
 
Participants randomized to Cohort 4, will visit the clinic on Days 1, 2, and 3 for dosing in an outpatient setting
	
Timepoint	Prescreening	Day 1	Day 2	Day 3	Day 4	Week 2 to 9 (weekly visits starting at Day 8)	EOS (last visit) Week 10, Day 64 ^b	Can be required due to AEs, and AESIs; follow-up of AEs and AESIs	
^b Day 64 or day of completion or premature discontinuation.
 
Participants will remain in the study until parasitemia or until Day 64, whichever comes first.
 
All EOS evaluations will be completed before providing antimalarial rescue treatment if required.
	
Blood films (microscopy)		X	X	X	X	X	X		
Thick and thin blood films will be collected at Visit 1 (predose) to confirm eligibility and at all visits.
 
Cohorts 1 to 3: The exact timepoints on Days 1 to 2 are provided in Table 2.
 
Cohort 4: Blood films should be examined at Screening, predose on Day 1, Day 2, and Day 3.
 
Blood sampling for parasitemia will be done simultaneously with PK.
	
Inclusion/ exclusion criteria		X								
COVID-19 antigen test		X							
The test will be conducted at Visit 1. Additional COVID-19 tests may be conducted as needed.
	
Demographic and medical history		X								
Randomization		X								

Assessments & Procedures	Outpatient	Outpatient/Inpatient ^a		Outpatient					Notes	
Visit Number	Prescreening	Scr + Visit 1 ^a	Visit 2 ^a	Visit 3	Visit 4	Visits 5 to 12	Visit 13	Unscheduled Visit	
^a Visit 1 and 2: Participants randomized to Cohorts 1 to 3 will remain in hospital or stay in the vicinity of the sites for 24 hours for PK sampling and assessment of parasitemia (see Table 2).
 
Participants randomized to Cohort 4, will visit the clinic on Days 1, 2, and 3 for dosing in an outpatient setting
	

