4.1 Overall Design

Study Design	Phase 2a, PoC, parallel, randomized, open label study (see Section 1.2)
Control Method	
• Randomization• Incidence rate of infection• Synthetic control cohort (Pyramax)
Single or Multicenter	Multicenter
Study Population Type	Adult and adolescent patients ≥ 12 to ≤ 55 years of age with asymptomatic P. falciparum malaria

Level and Method of Blinding	Open label
Bias Minimalization Method(s)	Evaluators blinded (microscopists and laboratory personnel performing the microscopy and PCR)
Study Intervention Assignment Method	Randomization stratified by site
Data and Safety Monitoring /Other Committee:	Yes (see Appendix 3)
Total Duration of Study Participation per Participant	
A maximum of 12 weeks (including a prescreening period of a maximum of 2 weeks). See Section 1.3.
 
Participants randomized to Cohorts 1 to 3 will be treated with a single dose of M5717 plus pyronaridine. Participants randomized to Cohort 4 will be treated with 3 daily and consecutive doses of Malarone.
 
Participants will be followed up until Day 64 (Week 10) or until recurrent infection, whichever occurs first.
 
Cohort 5 is a synthetic control cohort using external data from a completed clinical study that investigated the efficacy, safety, and tolerability of Pyramax in asymptomatic P. falciparum malaria patients (Dabira 2022). Data from participants treated with the 1-day Pyramax regimen and followed up until Day 64 will be used.

DMFA Substudy	The gametocidal activity of the M5717- pyronaridine combination will be assessed in vivo at selected sites (see Appendix 2)
Provisions for Study Extension or Entry into Roll-over Studies	Not applicable.

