4.4 End of Study Definition

The end of the study is defined as the date of the last participant last visit.

A participant has completed the study if he/she has completed all the study visits including the last visit or the last scheduled procedure shown in Section 1.3. If a participant has recurrent parasitemia

before the end of follow-up (Day 64, Week 10), they will attend the EOS Visit and will be considered as having completed the study.

5 Study Population

The study population consists of African adults and adolescents ≥ 12 years old, with asymptomatic *P. falciparum* infection. Potential participants will be identified by screening the local population for malaria.

The criteria in Sections 5.1 and 5.2 are designed to enroll only individuals who are appropriate for the study; thereby, ensuring the study fulfills its objectives. All relevant medical and nonmedical conditions are considered when deciding whether an individual is suitable for this study. Eligibility criteria for the substudy are provided in [Appendix 2](#).

Prospective approval of protocol deviations to inclusion and exclusion criteria, also known as protocol waivers or exemptions, is not permitted.

Before performing any study assessments that are not part of the individual's routine medical care, the Investigator will confirm that the individual has provided written informed consent, as indicated in [Appendix 3](#).

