	
 Single dose 660 mg M5717 plus 720 mg pyronaridine (≥ 65 kg) or 540 mg pyronaridine (≥ 45 to < 65 kg) (Cohort 3) 3 doses of Malarone (1,000 mg atovaquone plus 400 mg proguanil hydrochloride [proguanil]) to clear all parasites to measure the natural incidence of infection (Cohort 4) 
Intercurrent Event Strategy:
 
 Intake of rescue medication: composite variable strategy, i.e. endpoint is considered as failure (=positive blood smear at the time of rescue medication intake) Intake of antibiotics or other prohibited medication that impacts treatment effect (e.g. drug with antimalarial activity) at any timepoint: On-treatment strategy, i.e. time to parasitemia is censored at the time of antibiotics or prohibited medication intake Experience of any event that affects absorption (e.g. vomiting within the first 24 hours after dosing): Treatment policy strategy, i.e. treatment effect is estimated regardless of ICE. Death due to malaria: Composite variable strategy, i.e. parasitemia event is assumed at time of death. Death due to other reasons: On-treatment strategy, i.e. time to parasitemia is censored at the time of death 
Population-Level Summary HRs estimated from Cox' Proportional Hazards Model for each dose of M5717 compared to Cohort 4
	
Secondary	
Endpoint: Incidence of parasitemia (positive blood smear).
 
Population: See primary endpoint
 
Treatment: See primary endpoint
 
Intercurrent Event Strategy:
 
 Intake of rescue medication: composite variable strategy, i.e. endpoint is considered as failure (=positive blood smear at the time of rescue medication intake) Intake of antibiotics or other prohibited medication that impacts treatment effect (e.g. drug with antimalarial activity) at any timepoint: On-treatment strategy, i.e. time to parasitemia is censored at the time of antibiotics or prohibited medication intake Experience of any event that affects absorption (i.e. vomiting within the first 24 hours after dosing): Treatment policy strategy, i.e. treatment effect is estimated regardless of ICE Death due to malaria: Composite variable strategy Death due to other reasons: On-treatment strategy, i.e. time to parasitemia is censored at the time of death 
Population-Level Summary: Proportion of participants with parasitemia using Kaplan-Meier estimates for each dose of M5717 and for Cohort 4
	2

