	
Endpoint: Incidence of PCR-adjusted parasitemia (thick smear/microscopy, after adjustment for parasitemia due to new infections as determined by genotyping using PCR techniques).
 
Population: See primary endpoint
 
Treatment: See primary endpoint
	3

Objectives	Estimands/Endpoints	Ref. #
	
Intercurrent Event Strategy: See endpoint #2
 
Population-Level Summary: See endpoint #2
 
Endpoint: Incidence of PCR-adjusted parasitemia (thick smear/microscopy, after adjustment for parasitemia due to recrudescence as determined by genotyping using PCR techniques).
 
Population: see primary endpoint
 
Treatment: See primary endpoint
 
Intercurrent Event Strategy: See endpoint #2
 
Population-Level Summary: See endpoint #2
	4
To evaluate the parasite clearance time in adults and adolescents with asymptomatic P. falciparum malaria treated with different doses of M5717 in combination with pyronaridine	
Endpoint: Parasite clearance time defined as time from dosing to the first negative (no parasites) blood film (microscopy)
 
Target Population: See primary endpoint
 
Treatment: See primary endpoint
 
Intercurrent Event Strategy:
 
 • Intake of rescue medication after study treatment and before negative blood smear: treatment policy strategy, i.e. treatment effect is estimated regardless of ICE • Intake of antibiotics or other prohibited medication that impacts treatment effect (e.g. drug with antimalarial activity) at the time or after the time of study treatment, but before first negative blood smear: Treatment policy strategy • Experience of any event that affects absorption (i.e. vomiting within the first 24 hours after dosing): Treatment policy strategy, i.e. treatment effect is estimated regardless of ICE • Death before negative blood smear: On-treatment strategy, i.e. time to parasite clearance is censored at the time of death 
Population-level Summary: Median parasite clearance time as estimated by Kaplan-Meier method for each dose of M5717
	5
To evaluate the safety and tolerability of different doses of M5717 in combination with pyronaridine in adults and adolescents with asymptomatic P. falciparum malaria	Endpoint: Incidence, severity, and seriousness of TEAEs, treatment-emergent study intervention related AEs, as per CTCAE v 5.0	6

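### Kaplan-Meier proportions for PCR-adjusted recrudescence and new infection do not estimate the share of participants with each event, and together can exceed the any-parasitemia proportion

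*SAP*

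**What the plan says.** SAP 5 defines the summary for endpoint 2 as "Proportion of participants with parasitemia using Kaplan-Meier estimates for each dose of M5717 and for Cohort 4". Endpoint 3 (new infections adjusted out, so recrudescence remains) and endpoint 4 (recrudescence adjusted out, so new infection remains) each carry the entry "Population-Level Summary: See endpoint #2". SAP 14.2.2 adds that "the same analyses and outputs will be provided as for the primary estimand" and that the intercurrent-event strategies of 14.1.1 apply. It names no competing-event method.

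On follow-up, Protocol 4.1 states "Participants will be followed up until Day 64 (Week 10) or until recurrent infection, whichever occurs first", and the notes to Table 1 in Protocol 1.3 state "Participants will remain in the study until parasitemia or until Day 64, whichever comes first". Of participants with recurrent parasitemia before Day 64, Protocol 4.4 says "they will attend the EOS Visit and will be considered as having completed the study".

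On censoring, SAP 14.1.1 censors at an intercurrent event where the strategy calls for it, and otherwise "at the last available visit in case of premature study discontinuation or at the end of study in case no parasitemia event was observed". It has no separate rule for a recurrence of the other PCR type. The same section plans a table of counts and percentages of "parasitemia events (estimated directly from the data) will be provided together with estimates of a Kaplan-Meier (KM) analysis".

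**The concern.** A participant whose first recurrence is a new infection leaves follow-up at that visit. In the recrudescence curve this person has had no event, and the only rule that fits is censoring at end of study. The same holds the other way round. KM treats a censored person as still able to have the event later, at the rate seen in those who remain. One minus KM then describes a setting in which the other type of recurrence cannot happen. That is a net, hypothetical risk and not the proportion of participants who had the event, which is what SAP 5 names.

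The primary endpoint ignores genotype, so endpoints 3 and 4 are the efficacy endpoints that separate recrudescence from new infection. Protocol 4.2 wants to understand how far M5717 extends protection against new infections. If the two proportions in a report add to more than the any-parasitemia proportion beside them, that split is hard to read, and comparisons between cohorts with different event rates can be distorted.

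**Working it through.** **The plan's own figure.** The documents state no number for recrudescence or new infection. The planning rates come from Protocol 9.2: 63% (Cohort 4) and 87% (highest dose) free of parasitemia, HR 0.29, 21 events, 80% power. The Schoenfeld formula, 4(1.960 + 0.842)² / (ln 0.29)², gives 20.5, so 21 events; power at 21 events is 81% (two-sided alpha 0.05, 1:1). The stated design reproduces. The two proportions themselves imply ln 0.87 / ln 0.63 = 0.301, close to 0.29.

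**Inputs.** S is the proportion free of any parasitemia (0.63 or 0.87). s is the share of parasitemia that is recrudescence. The documents do not give s; I assume 0% to 50%, with cause-specific hazards proportional over time.

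**Formulas.**
- 1-KM: 1 − S^s for recrudescence, 1 − S^(1−s) for new infection.
- Cumulative incidence: s(1 − S) and (1 − s)(1 − S), which add to 1 − S.
- Excess of the KM sum over any parasitemia: the product of the two 1-KM values.

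| Cohort | s | Cumulative incidence (recrudescence + new = sum) | 1-KM (recrudescence + new = sum) | Excess on sum |
|---|---|---|---|---|
| 4 | 0% | 0 + 37.0 = 37.0% | 0 + 37.0 = 37.0% | 0 |
| 4 | 10% | 3.7 + 33.3 = 37.0% | 4.5 + 34.0 = 38.5% | 1.5 |
| 4 | 30% | 11.1 + 25.9 = 37.0% | 12.9 + 27.6 = 40.6% | 3.6 |
| 4 | 50% | 18.5 + 18.5 = 37.0% | 20.6 + 20.6 = 41.3% | 4.3 |
| Highest dose | 30% | 3.9 + 9.1 = 13.0% | 4.1 + 9.3 = 13.4% | 0.4 |
| Highest dose | 50% | 6.5 + 6.5 = 13.0% | 6.7 + 6.7 = 13.5% | 0.5 |

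(Sums are rounded after adding.) Worked case, Cohort 4 at s = 50%: 1 − 0.63^0.5 = 0.2063; 2 × 0.2063 = 0.4125; excess 0.2063² = 0.0425, about 1.9 of 45 participants.

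**Simulation** (45 participants, weekly visits, 6.25% dropout from 192 to 180; Cohort 4, s = 30%). KM gave 12.7% and 27.5%, Aalen-Johansen 11.1% and 25.9%, and crude percentages 10.7% and 25.1%. The sampling SD of the new-infection KM was about 7 points.

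**Timing.** If all recrudescences come before any new infection, the recrudescence KM is unbiased and new infection carries all the excess. For Cohort 4 at s = 30% it is 0.259 / (1 − 0.111) = 29.1% against 25.9%.

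**Higher transmission** (assumed 70% parasitemia, s = 30%): 30.3% + 57.0% = 87.3%, an excess of 17 points.

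**The case against.** Four arguments on the other side have weight.

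- **Crude percentages are already planned.** They sit in the same table, add up across types (apart from failures without a PCR type), and with about 6% dropout come close to cumulative incidence. This stands as a partial check. They are not, however, the population-level summary that SAP 5 names.
- **The target could be a net risk.** Adjusting for new infections can be read as asking what would happen without them. That is a legitimate target, but Protocol 9.4.1.1 works under ICH E9(R1), and neither document declares a hypothetical strategy for the other recurrence type. Cumulative incidence is not neutral between cohorts either, since more new infections leave fewer people to recrudesce. That is a reason to keep the cause-specific hazard ratios and a labelled 1-KM.
- **The censoring is inferred.** No sentence says that the other type is censored. This is true, and the silence itself needs repair.
- **The stakes are limited.** Protocol 9.1 makes all analyses descriptive, and neither the primary endpoint nor the hazard ratios are affected.

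A reader might infer that the bias is always largest in Cohort 4 and so flatters every dose. The documents do not support this without the missing share. Protocol 4.2 gives Malarone to clear all parasites, and with no recrudescence the bias in Cohort 4 is zero. Against a dose cohort with 13% parasitemia and s = 50%, Cohort 4 has the larger excess only if its own share is above 2.7%; against an assumed 25% and s = 50%, only above 11.9%. Nor are both proportions always overstated: if one type is absent there is no bias, and if one always comes first only the other is affected.

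**Conclusion.** The mismatch between estimator and stated quantity is real. As specified, 1-KM does not estimate the proportion of participants with recrudescence or with new infection. Whenever both types occur in a cohort (and not all at one visit), at least one proportion is too high and the two sum to more than endpoint 2.

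The size is modest at the planning rates. For an assumed recrudescence share of 0% to 50% with proportional hazards, the excess per endpoint is 0 to 2.1 points in Cohort 4 and 0 to 0.2 points at the highest dose, well below sampling error with 45 per cohort. At equal non-zero shares it is larger in Cohort 4, because its planned event rate is higher. This is a correction worth making before analysis, not a threat to the trial's main result.

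A related gap sits in the same section. Rescue medication counts as failure, and this carries over to endpoints 3 and 4 without reference to PCR type. Read literally, a rescued new infection is also a failure in the recrudescence analysis. If every recurrence were rescued, both Cohort 4 proportions would be 37% and sum to 74%. A reader might take that as the expected result. The documents do not support it: they give no rescue rate, and Protocol 6.8.1 leaves asymptomatic parasitemia to national guidelines or medical judgment. It does show that changing the estimator alone is not enough.

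**What to change.** In SAP 5 (endpoints 3 and 4) and SAP 14.2.2:

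1. Estimate the proportions by Aalen-Johansen cumulative incidence, with the other recurrence type as a competing event.
2. State that a recurrence of the other type is not an event for the endpoint, and how undetermined PCR results are handled.
3. In the analysis, count a rescue-medication failure only for the PCR type of the parasitemia that led to rescue. This concerns event coding, not who receives rescue.
4. Keep the Cox models, described as cause-specific.
5. Keep 1-KM as supplementary output, labelled as a net (hypothetical) risk.

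The cost is SAP wording and a little more programming with a standard procedure, on data already collected. The downside is that the main figure will not be directly comparable with reports that censor the other type; the supplementary 1-KM covers that.
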